## 1.0 TRIAL SUMMARY

Abbreviated Title	Pembrolizumab plus mitotane for adrenocortical carcinoma
Trial Phase	II
Clinical Indication	Recurrent/Metastatic Disease
Trial Type	Single arm, open label
Type of control	Historical control
Route of administration	Mitotane: PO. Pembrolizumab: IV
Treatment Groups	1
Number of trial participants	Up to 50
Estimated enrollment period	48 months
Estimated duration of trial	60 months
Duration of Participation	Up to 24 months
Estimated average length of treatment per patient	12 months

## 2.0 TRIAL DESIGN

### 2.1 Trial Schema

**Phase 2 trial of mitotane (MT) plus pembrolizumab (PEM) in advanced adrenocortical carcinoma (ACC)**

## 2.2 Schedule of Activities

**Table 1 Study Schedule of Activities**

	Screening	Lead-in phase	Treatment Period (cycles are 42 days) +/-5 -day window All CXD1 assessments may be performed up to 7 days before infusion					Progression	Study Completion /Early Termination Visit	Follow-Up 
Day	-28 through day -1	(Days 1-28 days $\pm$ 5)	C1 D1	C2 D1	C3 D1	C4 D1	C5D1 -last course h			
Informed consent	x									
Inclusion/exclusion criteria	x	x *								
Demographic data	x									
Pregnancy test 	x	x	x	x	x	x	x			
Physical Examination & ECOG PS 	x		x	x	x	x	x		x	
Routine labs 	x		x	x	x	x	x		x	
Fasting Lipid Panel 	x			x		x	x 			
Adrenal Hormones Panel 	x		x		x		x 			
Mitotane level 	x 		x	x	x	x	x		x	
12-lead ECG 	x									
Mitotane therapy 		x	x	x	x	x	x			

Pembrolizumab infusion 			x	x	x	x	x			
Response assessment 	x	x 	Scans will be done every 12 weeks (+/-7 days) starting on C2D1							
Concomitant medications	x		x	x	x	x	x		x	
Adverse events	x		x	x	x	x	x		x	x
Optional Biopsy	x					x		x		

 Pregnancy test, serum or urine at baseline, urine or blood within 72 hours prior to every cycle for women of child-bearing potential; All WOCBP must have a negative serum or urine pregnancy test within 72 hours prior to start of study drug.

 Physical examination at screening and day 1 of each cycle (+/- 7 days). ECOG performance status must be documented within 10 days prior to each cycle and can be obtained remotely or in person.

 Hemoglobin, hematocrit, platelet count, RBC count, WBC count, percent and absolute differential count, sodium, potassium, chloride, bicarbonate, glucose, BUN, creatinine, calcium, total and direct bilirubin, total protein, albumin, ALT, AST, alkaline phosphatase, TSH, free T4.

 Fasting Lipid panel at screening, Cycle 2, Cycle 4, and Cycle 6. May be repeated with every other cycle per treating physician discretion.

 Adrenal Hormones Panel: ACTH, Cortisol, plasma renin activity, plasma aldosterone concentration, DHEA-Sulfate, testosterone (in women), estradiol (in men and postmenopausal women), and 11-deoxycortisol. All patients must have full hormonal evaluation at screening. Adrenal Hormonal labs may be repeated (complete or partial panel) every other cycle starting Cycle 1 per treating physician discretion.

 Serum mitotane level: Only patients who are already on mitotane at time of screening will have mitotane level checked during screening. Otherwise, mitotane level will be checked cycles 1-5 with the option of having mitotane levels checked every other cycle starting Cycle 5 per treating physician discretion.

 All patients will undergo 12-lead EKG at screening. Further, evaluation of EKG can be repeated with other cycles per treating physician discretion.

 Patients who were on mitotane prior to consent and meet eligibility criteria do not need to have lead-in phase (including leading phase assessments) and can start on combination therapy if completed 28 days of mitotane therapy

 Patients will be treated for a maximum of 18 cycles with pembrolizumab but may continue mitotane beyond the 18 cycles per treating physician discretion outside the clinical trial

 Response assessment by cross-sectional imaging such as CT, MRI, or PET-CT as per standard of care for each patient. Screening assessment must occur within 28 days prior to lead-in phase and imaging to be repeated within 7 days of Cycle 1 Day 1 of combination therapy. PET/CTs may be substituted for CT or MRI at baseline and re-staging, if in the opinion of the treating physician.

 Response assessment by cross-sectional imaging will consider baseline scan as the study done within 7 days of Cycle 1 Day 1 of combination therapy.

 All patients who discontinue treatment without objective disease progression will be followed up with tumor assessment every 12 weeks ( $\pm$ 14 days) or as determined by the principal investigator or designee) until disease progression or the start of a different anti-cancer therapy. Survival follow-up via phone call, medical record review, or visit with physician will occur every 3 months for 2 years once they are off study treatment or until patient death, withdrawal of consent, patient is lost to follow-up, or study termination, whichever occurs first.

\* Please refer to Table 5. The lead-in phase is primarily designed to ensure patients safety and to have initial evaluation of potential AEs attributed to MT use with particular attention to liver enzymes. If MT use caused elevated ALT or AST during the lead-in phase not meeting eligibility criteria for LFTs or if participants developed  $\geq$  G3 non-hematological toxicity, then these patients will not go through the combination therapy and may come off protocol at the discretion of the PI and will be replaced if excluded by other patients and considered as screen failure. Patients who were on prior MT therapy must complete 28 days of MT use prior to moving to combination therapy and must meet eligibility criteria stated at screening phase and will not need to have the lead-in phase assessment.

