#### **6.1.7.3.2 Efficacy Follow-up Visits**

All patients who discontinue treatment without objective disease progression will be followed up with tumor assessment every 12 weeks ( $\pm 14$  days) or as determined by the principal investigator or designee) until disease progression or the start of a different anti-cancer therapy. Survival follow-up via phone call, medical record review, or visit with physician will occur every 3 months for 2 years once they are off-study treatment or until patient death, withdrawal of consent, patient is lost to follow-up, or study termination, whichever occurs first.

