#### **6.1.7.3.3 Survival Follow-up Contacts**

Participant survival follow-up status will be assessed approximately every 12 weeks to assess for survival status until death, withdrawal of consent, or the end of the study, whichever occurs first.

The first survival follow-up assessment should be scheduled as described below:

- For participants who discontinue treatment intervention and who will not enter the Efficacy Follow-up Phase, the first survival follow-up contact will be scheduled 12 weeks after the discontinuation visit and/or safety follow-up visit (whichever is last).

For participants who completed assessments in the Efficacy Follow-up Phase, the first survival follow-up contact will be scheduled 12 weeks after the last efficacy assessment follow-up visit has been performed.

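### Survival follow-up has two conflicting end rules, and the 2-year rule makes OS censoring depend on how long a patient was treated

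*Combined protocol and SAP*

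**What the plan says.** Five places share one rule: Table 1 footnote 12, Table 2 footnote 2, Table 3 footnote 2, the post-treatment text in Section 6.1.7.2, and Section 6.1.7.3.2. Footnote 12 says survival contacts "will occur every 3 months for 2 years once they are off study treatment"; Section 6.1.7.3.2 says they "will occur every 3 months for 2 years once they are off-study treatment". In all five, contacts stop sooner at death, withdrawal of consent, loss to follow-up or study closure. Footnote 12 ends: "patient is lost to follow-up, or study termination, whichever occurs first".

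Section 6.1.7.3.3, which is dedicated to survival contacts, schedules them approximately "every 12 weeks to assess for survival status until death, withdrawal of consent, or the end of the study, whichever occurs first". It has no limit counted from the end of treatment.

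Sections 3.2 and 4.2.3.1 start OS at combination therapy. Section 7.0 says only that OS is analysed with Kaplan-Meier curves. It gives no OS censoring rule, data cut-off or landmark time.

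Section 1.0 gives 48 months of enrolment, 60 months under "Estimated duration of trial", at most 24 months under "Duration of Participation", and an average of 12 months on treatment.

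**The concern.** For a survivor more than 2 years off treatment while the study is open, one rule ends contact and the other continues it. Staff following different sections would collect different OS data on the same patient. Section 5.6 requires data through the last scheduled follow-up, so the choice of rule decides what must be collected.

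The 2-year rule also has a statistical cost. Its clock starts when treatment stops, but the OS clock starts with combination therapy. Progression is one of the reasons for stopping treatment in Section 5.6, so survivors censored earliest under this rule will tend to be those who progressed early. Kaplan-Meier assumes that censoring is unrelated to prognosis. If it is related, the late part of the curve rests increasingly on patients who were treated for longer.

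**Working it through.** **1. The plan's own figure.** Enrolment 48 months + average treatment 12 months = 60 months, the stated trial duration. It reproduces.

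**2. Censoring time under the 2-year rule.** Measured from the start of combination therapy, a survivor is censored at treatment duration + 24 months, or at study closure if earlier:

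| Months on treatment | Censored at month |
|---|---|
| 3 | 27 |
| 12 | 36 |
| 24 | 48 |

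No one is censored by this limit before month 24, so the curve up to that point is untouched. Under Section 6.1.7.3.3 the only planned censoring is at study end, which does not depend on treatment duration.

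**3. Size of the bias.** The documents give no joint model for treatment time and survival, so these inputs are assumptions. All models use uniform entry over 48 months and closure at month 60.

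- *Model A.* 75% of patients have a median PFS of 4.1 months (the mitotane-alone figure in Section 4.1) and 25% have 24 months. Median survival after progression is 10 months, and treatment ends at progression or after 18 cycles. True OS at 36 and 48 months is 24.1% and 14.7%. Kaplan-Meier under the 2-year rule gives 26.4% and 19.4%, a bias of 2.3 and 4.7 points. Under Section 6.1.7.3.3 it gives 24.1% and 14.7%. At 36 months about 4 rather than 6 of 50 patients remain at risk.
- *Model A, weaker contrast.* With a 12-month median in the 25% subgroup, the 36-month bias is about 1.3 points. With one population at 4.1 months it is about 0.2 points, and it stays below 1 point at 48 months.
- *Model B.* Mean treatment is 12 months, capped at 24. Survival after treatment is exponential with mean 6 + b × treatment months:

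| b | True OS, 36 mo | 2-year rule | Bias (points) | True OS, 47 mo | 2-year rule | Bias (points) |
|---|---|---|---|---|---|---|
| 0.5 | 0.196 | 0.201 | 0.5 | 0.098 | 0.107 | 0.9 |
| 1 | 0.291 | 0.300 | 0.9 | 0.184 | 0.205 | 2.1 |
| 2 | 0.408 | 0.424 | 1.6 | 0.303 | 0.342 | 3.9 |

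In Model B, when survival after treatment is unrelated to treatment time, the bias is nil. Closing at month 60 produces no bias by itself.

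**4. Participation figure.** Lead-in 28 days + 18 cycles × 42 days = 28 + 756 = 784 days; 784 / 30.4375 = 25.8 months, which exceeds 24. Adding 2 years of follow-up gives 25.8 + 24 = 49.8 months.

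**5. Calendar.** Two full years after treatment, completed by month 60, require entry by month 60 − (treatment duration + 24). Ignoring the lead-in:

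| Months on treatment | Latest entry (month) | Share of uniform accrual |
|---|---|---|
| 3 | 33 | 33/48 = 69% |
| 6 | 30 | 30/48 = 62.5% |
| 12 | 24 | 24/48 = 50% |
| 24 | 12 | 12/48 = 25% |

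No one entering after month 60 − 24 = 36 can receive the full 2 years. With mean treatment of 12 months, about half of all patients could.

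**The case against.** A reader might infer that the 60-month trial length breaks the follow-up plan. The documents do not support that. The five passages all stop at study termination, and Section 6.1.7.3.3 stops at the end of the study, so closing at month 60 complies with both rules. The 60 months also follow from the plan's own enrolment and treatment figures. What remains is a shortfall for late entrants against the 2 years described.

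A reader might also take the upward bias as established. It is conditional. It needs treatment duration to predict later survival, and its size comes from inputs that the protocol does not supply. Model A's mean treatment is about 8.8 months, against the protocol's 12. Even in Model A, the 36-month estimate from 50 patients has a standard deviation of about 8 points, against a 2.3-point bias. Its 48-month estimate rests on about 1.2 patients at risk. Median OS in that model is about 20 months, before the limit acts. OS is secondary and descriptive, with no planned test or late landmark.

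The participation figure may simply mean treatment time, since Section 5.2.1 describes 18 cycles as a maximum of 2 years. If so, it needs a label.

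Finally, the contradiction could be removed by bringing Section 6.1.7.3.3 into line with the other five passages. That would give one rule but keep the treatment-dependent censoring. Reporting OS only to month 24 would avoid the bias but leave later survival undescribed.

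These points limit the size of the concern. They do not resolve the contradiction or the way the 2-year rule sets the censoring time.

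**Conclusion.** The contradiction is certain: five passages have the limit and one does not. That the 2-year rule ties planned censoring to treatment duration follows directly from the definitions. The resulting bias is conditional and confined to the curve after month 24. It is about 0.2 to 2.3 points at 36 months. It is about 1 to 5 points at 47 to 48 months where treatment duration and later survival are appreciably linked, and less where they are not. Fewer patients also remain at risk late on. A link is plausible because progression ends treatment, but the documents do not quantify it. The ORR and toxicity decisions are unaffected.

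The 24-month participation entry cannot cover lead-in plus 18 complete cycles, still less survival follow-up. The 60-month duration is not an error. The point merits correction because late survival contacts that are not made may not be recoverable.

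**What to change.** - Use the Section 6.1.7.3.3 rule in all six places. Follow every treated patient for survival until death, withdrawal of consent, loss to follow-up or one common study cut-off. Delete the 2-year limit counted from end of treatment from the Table 1, 2 and 3 footnotes and from Sections 6.1.7.2 and 6.1.7.3.2. Add loss to follow-up to Section 6.1.7.3.3, which does not name it.
- State in Section 7.0 that patients not known to have died are censored for OS at the date last known alive or at the common cut-off, whichever is earlier.
- In Section 1.0, restate the participation figure so that it includes follow-up, or label it as treatment duration.

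The cost is wording in a few places, plus a small number of extra phone or record-review contacts for patients alive more than 2 years after stopping treatment. All fall within the existing study period.

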**Table 2 Study Schedule of Activities: Survival Status**

Study Period	Screening Phase	Lead-in phase	Treatment Cycles (6-Week Cycles) 						EOT	Post Treatment Visits 		Notes:
Treatment Cycle	Screening (Visit 1)		1	2	3	4	5	6 to 18	DC	Safety Follow-up	Survival Follow-up	
Scheduling Window (Days):	-28 to -1	Days 1-28 days ( $\pm$ 5)	$\pm$ 5	$\pm$ 5	$\pm$ 5	$\pm$ 5	$\pm$ 5	$\pm$ 5	Time of DC	30 Days from the last dose ( $\pm$ 7 days)	Every 12 Weeks ( $\pm$ 14 days)	
Subsequent Anti-neoplastic Therapy Status									X	X		

11

Patients will be treated for a maximum of 18 cycles with pembrolizumab but may continue on mitotane beyond the 18 cycles per treating physician discretion outside the clinical trial.

All patients who discontinue treatment without objective disease progression will be followed up with tumor assessment every 12 weeks ( $\pm 14$  days) or as determined by the principal investigator or designee until disease progression or the start of a different anti-cancer therapy. Survival follow-up via phone call, medical record review, or visit with physician will occur every 3 months for 2 years once they are off-study treatment or until patient death, withdrawal of consent, patient is lost to follow-up, or study termination, whichever occurs first.

**Table 3 Study Schedule of Activities: Tumor Imaging**

Study Period:	Screening Phase	Lead-in phase	Combination Treatment Cycles (6-Week Cycles)						End of Treatment	
Treatment Cycle/Title  :	Screening (Visit 1)	28 days	1	2	3	4	To be repeated beyond 6 cycles		Discon	Survival Follow-Up
							5	6		
 Scheduling Window (Days):	-28 to -1	X 		$\pm 7$		$\pm 7$		$\pm 7$	At time of discontinuation $\pm 7$	 Every 12 weeks post discontinuation $\pm 14$

 Baseline assessment must occur within 28 days prior to day 1 of lead-in phase. After baseline assessment during screening, scans will be done during the lead-in phase within 7 days of combination therapy and then every 12 weeks (+/-7 days) starting on C2D1. Response assessment by cross-sectional imaging such as CT, MRI, or PET-CT as per standard of care for each patient. PET/CTs may be substituted for CT or MRI at baseline and re-staging, if in the opinion of the treating physician.

All patients who discontinue treatment without objective disease progression will be followed up with tumor assessment every 12 weeks ( $\pm 14$  days) or as determined by the principal investigator or designee until disease progression or the start of a different anti-cancer therapy. Survival follow-up via phone call, medical record review, or visit with physician will occur every 3 months for 2 years once they are off-study treatment or until patient death, withdrawal of consent, patient is lost to follow-up, or study termination, whichever occurs first.

 Patients who start with lead-in phase need to have imaging within 7 days of C1D1 of combination therapy as a baseline to assess response to therapy. Patients who were on mitotane prior to consenting will not need lead-in phase and will go directly to combination therapy and the screening phase imaging will be considered the baseline for future tumor measurement.

### **3.0 OBJECTIVE(S), HYPOTHESIS(ES), AND ENDPOINT(S)**

#### **3.1 Primary Objective(s), Hypothesis(es), and Endpoint(s)**

(1) **Objective:** Assess the clinical efficacy of the combined use of MT with PEM in patients with advanced ACC.

**Hypothesis:** We hypothesize that adding PEM will enhance the clinical efficacy of MT. This additive/synergistic effect could be related to the intrinsic adrenolytic activity of MT that could lead to antigens exposures to immune cells. Furthermore, the cortisol lowering effect of mitotane is expected to alter the tumor microenvironment leading to a change the milieu of the tumor infiltrating immune cells to make ACC more susceptible to PEM. Also, cortisol lowering can reduce lymphocytes inhibition and enhances the efficacy of PEM.

**Primary Endpoint:** Overall response rate (ORR) assessed objectively using RECIST 1.1 criteria defined as the percentage of patients who have a partial or complete response to the combined treatment of MT plus PEM

#### **3.2 Secondary Objective(s), Hypothesis(es), and Endpoint(s)**

(1) **Objective:** Evaluate the safety and efficacy of the combined use of MT plus PEM in patients with advanced ACC.

**Hypothesis:** The optimal MT plasma levels have not been established prospectively in metastatic ACC. We hypothesize that mitotane level of 14-20 mg/L is associated with oncological responses, but we also anticipate that the combined use of PEM MT could be associated with responses at lower levels of MT which might be associated with more favorable AE profile of MT.

**Secondary Endpoints:**

1. Overall survival (OS), defined as the time from combination therapy to death from any cause.
2. Progression Free Survival (PFS), defined as the time from the start of combination therapy phase to disease progression or death from any cause.
3. Explore the association between MT level and response to therapy
4. Safety assessment by the Common Terminology Criteria for Adverse Events (CTCAE) V5.0

#### **3.3 Exploratory Objective(s)**

(1) **Objective:** Correlate safety and efficacy data with steroid profile, immune markers and MT levels.

1. Obtain optional tumor biopsy prior to, during, and after treatment with MT/PEM combination to study immune markers such as infiltrating tumor lymphocytes, and other immune markers during therapy.
2. Study the changes in circulating markers (MT level, immune cytokines, steroid profile) in blood samples obtained prior to, during, and after treatment with MT/PEM combination

## 4.0 BACKGROUND & RATIONALE

### 4.1 Background

Adrenocortical carcinoma (ACC) is a rare endocrine malignancy with high recurrence rates and mortality. ACC has an annual incidence of about 1-2 cases per million (Else T et al. Endocr Rev. 2014). ACC patients often cluster in few centers across the world with known experience in managing this disease. Currently, ACC patients receive systemic therapy that has suboptimal and short-lived benefit.

Mitotane (MT) (Lysodren®) (o,p'-DDD or 1,1-dichloro-2[o-chlorophenyl]-2-[p-chlorophenyl]ethane) is a pesticide isomer that is directly toxic to adrenocortical cells. MT is a unique drug with dual benefit in ACC. MT has an adrenolytic activity in addition to its ability to block steroidogenesis enzymes and thus it reduces circulating cortisol levels. Furthermore, MT changes the peripheral metabolism of cortisol and reduces circulating cortisol levels. MT is administered orally in tablets of 500 mg. MT is the only FDA-approved drug to treat advanced ACC and considered the standard of care in these patients. MT has been in use for almost 5 decades and is associated with objective response rate of 11-20.5% and median progression free survival of 4.1 months (Reidy-Lagunes et al. 2017; Megerle et al. 2018). MT is often combined with cytotoxic chemotherapy. The most commonly used regimen is (etoposide, doxorubicin, and cisplatin) [MT-EDP]. This regimen is associated with response rate of 23% with median time to progression of about 5 months while 58% of patients had serious AEs (Fassnacht et al. 2012). Considering the limited efficacy and the high toxicity of the commonly used therapy (MT-EDP), the lack of highly effective second line therapy, and the paucity of available clinical trials for ACC patients, there is a critical unmet need to provide an effective and less toxic systemic therapy to ACC patients as an alternative to MT-EDP.

Pembrolizumab is a potent humanized immunoglobulin G4 (IgG4) monoclonal antibody (mAb) with high specificity of binding to the programmed cell death 1 (PD-1) receptor, thus inhibiting its interaction with programmed cell death ligand 1 (PD-L1) and programmed cell death ligand 2 (PD-L2). Based on preclinical in vitro data, pembrolizumab has high affinity and potent receptor blocking activity for PD-1. Pembrolizumab has an acceptable preclinical safety profile and is in clinical development as an intravenous (IV) immunotherapy for advanced malignancies. **Keytruda®** (pembrolizumab) is indicated for the treatment of patients across a number of indications because of its mechanism of action to bind the PD-1 receptor on the T cell. For more details on specific indications refer to the Investigator brochure (IB).

